operation, at baseline and throughout the study: **Minnesota Nicotine Withdrawal Scale** (MNWS; 31) to monitor symptoms of tobacco withdrawal; **Questionnaire of Smoking Urges-Brief** (QSU-Brief; 32) to measure cravings to smoke; the **TLFB for Alcohol and Drug Use** (33,24); the **Nicotine Use Inventory** (NUI; 4, 27) is a brief questionnaire that has been used throughout the varenicline Phase III-IV trials that monitors smoking rates and probes for other forms of nicotine use including e-cigarettes, hookah, cigars, etc; the **Hospital Anxiety and Depression Scale** (HADS; 35) is comprised of two separate 7-item self-report questions assessing anxiety and depressive symptoms, respectively; the **Altman Self-Rating Mania Scale** (ASRM; 36) is a 5-item self-rating mania scale with a scoring range from 0-20 that assesses symptoms of mania and hypomania; the **Columbia-Suicide Severity Rating Scale** (C-SSRS; 37) is a semi-structured interview conducted by trained raters to monitor suicide ideation and behaviors; the **Insomnia Severity Index** (ISI; 38) is a reliable and valid 7-item self-report measure to evaluate perceived sleep difficulties; the **Avoidance and Inflexibility Scale** (AIS; 41) is a 27-item questionnaire measuring changes in acceptance-based processes of smoking cessation based on this technique's hypothesized mechanism of action; the **Neuropsychiatric Adverse Events Interview** (NAEI) is a 25-item questionnaire that was used in EAGLES (4) and our prior work (27) to probe for neuropsychiatric complaints that might qualify as adverse events in a clinical trial; an **Assessment of General AEs** using standard operating procedures to record AEs according to the Medical Dictionary for Regulatory Activities version 18.0 (MedDRA; 44) – derived preferred terms; and the **Self Efficacy Questionnaire** (SEQ-12; 42) and **Confidence to Quit Scale** (43) measuring participants' self-efficacy and confidence to quit smoking. Study medication will be dispensed to participants by mail per VMRF pharmacy's shipping protocol with instructions on its use. Participants will also have their first session of ACT session (see below) at their week 0 baseline visit. All assessments will be performed by telephone (on HIPAA compliant Doximity) as scheduled with the exception of vitals, urine or blood collection, and exhaled CO which will not be collected during this Red phase.

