2° Efficacy Outcome: In keeping with the pilot nature of this trial, we will use 7-day point prevalence abstinence (PPA) at week 12 confirmed by expired CO levels ≥ 4 ppm and urine cotinine levels < 200 mg/ml as the secondary efficacy endpoint. We will continue to track smoking outcomes through week 24 using these same biochemical verification measures to assess 7-day PPA at week 24 as a tertiary outcome.

Other Secondary Outcome Measures: Our gathering of data on the MNWS, QSU-Brief, ISI, SEQ-12, Confidence to Quit Scale is exploratory in nature and is intended to provide preliminary information on the mechanism of action of combined varenicline and ACT in SMI smokers and their relation to NPSAEs. We will also explore ACT's effects on avoidance and inflexibility with the AIS at weeks 12 and 24.

Determination of the NMR: The ratio of trans-3'-hydroxycotinine (3HC) and cotinine (COT) will be measured in plasma using electrospray ionization liquid chromatography tandem mass spectrometry (ESI LC-MS/MS) technology adapted from the protocols described by Tanner et al. (45) and Lerman et al. (7). COT and 3HC in plasma will be determined by quantifying with standard deuterium labeled COT and 3HC, known as COT-d3 and 3HC-d3 (commercially available from Sigma-Aldrich). Plasma samples will be spiked with a known amount of COT-d3 and 3HC-d3, and samples will be subjected to MS to quantitate the endogenous levels of COT and 3HC by parallel reaction monitoring. LC-MS/MS will be performed on the high-resolution Orbitrap Q-Exactive LC -MS system located in the [name] lab in the Skaggs School of Pharmacy and Pharmaceutical Sciences. Standard plots of different amounts of deuterated and non-deuterated COT and 3HC standards into control plasma, followed by LC-MS/MS, will define the linear range of quantitative measurements, lower limit of detection, and reproducibility of replicate samples. Ratios of 3HC/COT will be calculated from quantitative MS data analyzed by the Skyline software. Reliability of these procedures in plasma is high with NMR measurements robust even to differences in analytic methods used by different laboratories (45). The NMR data will be compiled with the phenotypic data of this study to examine the relationship of NMR to NPSAEs and smoking cessation.

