10. HUMAN SUBJECTS

Sixty men and women with DSM-V BD (Type I or Type II, N = 30) or SSD (schizophrenia or schizoaffective disorder, N = 30) and who are chronic smokers will be recruited to participate in this pilot trial at Pac-TARC, which is a research center housed within the UCSD Department of Psychiatry. With an anticipated 33% screen failure rate, we anticipate screening up to 90 participants to accrue the sample. Each group will include ~ 50% women and individuals of any ethnic background are eligible to participate. Based on our prior work recruiting for EAGLES in San Diego where 35% (182/523) of those phone-screened self-identified as BD or SSD smokers, we expect that the SMI smokers who call to inquire about the study will have demographic and clinical characteristics similar to those SMI smokers enrolled in EAGLES (e.g., ~47% female, 65% White). Also, like EAGLES, we expect BD and SSD smokers to have similar baseline smoking characteristics.

Inclusion Criteria

- 18-70 years of age
- Outpatients with a DSM-V diagnosis of BD or SSD
- Smoke at least 10 cigarettes per day and have an expired carbon monoxide (CO) breathalyzer of \geq 10 ppm at screening and baseline visits
- Are motivated to quit smoking by scoring 5 or higher on the Contemplation Ladder (28)
- Have access to a mental health provider should their condition worsen during study enrollment

Exclusion Criteria

- Females who are pregnant, planning to become pregnant, or lactating
- Test positive for any non-prescribed medications (e.g., opiates, benzodiazepines, psychostimulants) or illicit drugs excluding cannabis during screening
- Have made a suicide attempt or engaged in self-mutilatory behavior in the past year
- Meet criteria for another SUD in the past month
- In the investigators' judgement, are either psychiatrically (e.g., presently manic, hypomanic, acutely psychotic, depressed or suicidal) or medically (e.g., uncontrolled hypertension, angina) unstable to safely participate
- Are currently using any other form of treatment for smoking cessation

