13. ALTERNATIVES TO STUDY PARTICIPATION

Participants do not have to be in this study to receive treatment for their smoking habit. Instead of taking part in this study, they may choose to receive treatment with medications that have been approved for use in this country or they may choose non-drug therapies. If a participant would like referrals or does not want to continue in the study, the following is a list of alternative treatments that would be recommended after talking with one of the study doctors. The study doctor will discuss the risks and benefits of the alternative treatments including: Nicotine gum, Nicotine patch, Nicotine inhaler, Nicotine spray, Nicotine lozenge, Bupropion, Hypnosis, "Cold turkey", and Counseling/Self-help other than ACT.

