During the course of the study, safety data will be collected for all subjects who have enrolled into the study. Participants will receive an Emergency Contact Information card in case they need to reach study doctors outside the working day. The incidence and severity of treatment-emergent Adverse Events (AEs) will be assessed at each in-person and telephone visit by trained study staff members. Further, the Neuropsychiatric Adverse Event Interview (NAEI) will be conducted at each in-person visit by a trained interviewer, which will also assess changes in psychiatric symptoms. The professional, experienced staff members conducting the clinical assessments and venipuncture will be sensitive to any patient discomfort and will make every effort to minimize aggravation by taking breaks or discontinuing the assessment if necessary. Similarly, trained therapists delivering ACT will discuss any study issues as they arise with participants as part of the therapy. Participants may withdraw from the study at any time at their own request, or they may be withdrawn at any time at the discretion of the investigators for safety, behavioral, or administrative reasons. If a subject does not return for a scheduled visit, every effort will be made to contact the participant. In any circumstance, every effort will be made to document the outcome, if possible. The principal investigator will inquire about the reason for withdrawal, request that the participant return for a final visit, if applicable, and follow-up with the participant regarding any unresolved AEs. On the day of randomization, participants are given an emergency notification card. The emergency notification card has a 24-hour emergency number by which to contact a clinical study staff member in case of an after-hours emergency. Participants who discontinue treatment will be encouraged to continue participation in the study and all planned assessments/evaluations. Specifically, they will maintain the visit schedule and should continue participation through the non-treatment follow-up phase of the study. All participants who permanently discontinue study drugs for any reason will remain in the study as Off Treatment and In Study (OTIS). Every effort will be made to keep the subject in the study until the final visit and all planned assessments/evaluations should be performed. Specifically, the subject will maintain the visit schedule and continue participation through the non-treatment follow-up phase of the study.

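### The cotinine test required to confirm abstinence at weeks 12 and 24 can score a tobacco-abstinent user of nicotine replacement as a smoker

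*Combined protocol and SAP*

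**What the plan says.** The paragraph on the 2° Efficacy Outcome in Section 9 defines 7-day PPA at week 12 as "confirmed by expired CO levels ≥ 4 ppm and urine cotinine levels < 200 mg/ml as the secondary efficacy endpoint". Week 24, a tertiary outcome, follows the same rule: "We will continue to track smoking outcomes through week 24 using these same biochemical verification measures to assess 7-day PPA at week 24". Both tests must be passed, and nothing is said about nicotine that does not come from tobacco.

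Four other places bear on this:

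- Section 7, on the nicotine metabolite ratio, describes cotinine as the breakdown product of nicotine.
- Section 10 excludes, at entry, people who "Are currently using any other form of treatment for smoking cessation". I found no corresponding restriction after randomization.
- Section 13 reads "If a participant would like referrals or does not want to continue in the study, the following is a list of alternative treatments", and the list includes "Nicotine gum, Nicotine patch, Nicotine inhaler, Nicotine spray, Nicotine lozenge, Bupropion".
- Section 15 states "All participants who permanently discontinue study drugs for any reason will remain in the study as Off Treatment and In Study (OTIS", and asks that their planned assessments continue through the follow-up phase.

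The information needed to recognise these participants is collected. The Nicotine Use Inventory (NUI) "probes for other forms of nicotine use including e-cigarettes, hookah, cigars, etc", and concomitant medications are recorded repeatedly (Table 3). No text links either form to the abstinence rule.

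**The concern.** PPA is meant to measure whether a person has stopped smoking. Cotinine shows nicotine intake whatever its source. A participant who stops varenicline, takes up a patch or lozenge and stops smoking has the outcome of interest, yet may fail the cotinine test because of the product being used to stay abstinent.

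Two consequences follow. First, PPA is understated. Section 9 sets PPA beside EAGLES rates of 28.2% at week 12 and 20.0% at week 24 and intends it to guide later studies. Second, the understatement could differ by arm. People who stop study drug have a reason to seek another aid, and the protocol's own Table 2 shows more stopping for adverse events on the standard dose. Any resulting difference would flatter the low dose. At week 24 every participant is off study drug, so uptake of other products is then not confined to early stoppers.

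**Working it through.** The plan derives no figure from this rule, so there is none to reproduce. The check applies the rule to individual cases and then sizes the effect.

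**1. What the printed limits do.** 200 mg/ml = 200 × 1,000,000 = 200,000,000 ng/ml. No urine sample will plausibly reach that, so the cotinine limit as printed fails nobody. The CO limit as printed (at or above 4 ppm) runs the wrong way for confirming abstinence. These are separate errors. The rest assumes that CO is an upper limit and cotinine is in ng/ml.

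**2. Cases under that reading, all tobacco-abstinent.**

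| Participant | CO | Cotinine | Scored |
|---|---|---|---|
| No other aid | passes | passes | abstinent |
| Bupropion | passes | passes | abstinent |
| Nicotine replacement, cotinine below 200 | passes | passes | abstinent |
| Nicotine replacement, cotinine 200 or above | passes | fails | smoker |

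Only the last row is wrong. The documents give no cotinine levels for users of nicotine products, so how often it arises cannot be worked out from them.

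**3. Cost per person.** 1/30 = 3.3 points within an arm; 1/60 = 1.7 points overall. From a true week-24 PPA of 20.0% (12/60), losing 1, 2 or 3 people gives 11/60 = 18.3%, 10/60 = 16.7% or 9/60 = 15.0%.

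**4. Illustration of a difference between arms.** Inputs:

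- Stopping for adverse events: 14.0% low dose, 21.7% standard dose (Table 2, smokers without mental illness). With 30 per arm this is 4.2 and 6.5 people.
- Uptake of nicotine replacement among them: 100% (assumption).
- Abstinence on a nicotine product: 10.8% and 15.2%, the end-of-treatment PPA for EAGLES patch users with bipolar and schizophrenia-spectrum disorders (Section 9, description of the ACT intervention).
- All of them are retained, assessed and at or above the cotinine limit (assumption).

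Points of PPA lost = stopping rate × uptake × abstinence rate.

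| Abstinence rate | Low dose | Standard dose | Gap |
|---|---|---|---|
| 10.8% | 14.0 × 0.108 = 1.5 | 21.7 × 0.108 = 2.3 | 0.8 |
| 15.2% | 14.0 × 0.152 = 2.1 | 21.7 × 0.152 = 3.3 | 1.2 |

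The highest patch rates in the protocol are 33% and 40%, from the preliminary study of ACT plus patch in bipolar smokers. Still at full uptake, they would give gaps of 7.7 × 0.33 = 2.5 and 7.7 × 0.40 = 3.1 points, where 7.7 = 21.7 − 14.0.

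**5. Against sampling error.** At 20% PPA and 30 per arm, the standard error of the difference between arms is √(2 × 0.20 × 0.80 / 30) = 0.103, about 10 points.

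**The case against.** The strongest reply is that a double biochemical test is a recognisable, strict choice where no nicotine product is study treatment, and that little rests on it here. PPA is secondary at week 12 and tertiary at week 24, Section 9 says the trial is not powered for clinical outcomes, no formal testing is planned, and the illustrated gap is roughly a tenth of its standard error. Alternative scoring could also be done later from forms already completed. All of this stands as a limit on importance. It does not make the rule right: strictness about smoking is a choice, but failing a non-smoker for using nicotine replacement is a wrong classification. Settling the rule before analysis also avoids case-by-case decisions.

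Several stronger readings are tempting, and the documents do not support them:

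- *Users of nicotine replacement are always counted as smokers.* This needs the ng/ml reading and a level at or above the limit. The documents support only that they can be.
- *Counting an abstinent bupropion user as a quitter is a matching error.* It is not. That person has stopped smoking, which is what PPA measures.
- *The protocol sends participants to nicotine products and then keeps them in the trial.* Section 13 concerns alternatives to participation and applies to people who want referrals or do not want to continue. Section 15 retains people who stop study drug. The groups can overlap, but no passage says that a referred participant on nicotine replacement stays in. Those who leave the study have no visit to misclassify.
- *The spurious gap is 1.9 to 3.9 points.* That requires 25% to 50% of stoppers to be abstinent on a nicotine product. Both figures exceed the EAGLES patch rates, and 50% exceeds every patch rate in the protocol.

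**Conclusion.** The point holds as a limited defect in the outcome definition. With the cotinine limit read in ng/ml, the rule can score a tobacco-abstinent user of nicotine replacement as a smoker at either time point. The cost is 3.3 points of PPA per person in an arm, or 1.7 overall.

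The number of people is unknown. The illustration gives losses of about 1.5 to 2.1 points on low dose and 2.3 to 3.3 on standard dose, a gap of about 0.8 to 1.2 points in favour of low dose. It rests on stopping rates from smokers without mental illness, full uptake, complete retention, and patch abstinence rates from people who were not early stoppers of varenicline. It covers only stopping for adverse events and does not model uptake after week 12, for which the documents give no data. A reader might infer that week 24 is worse affected. That is plausible but not shown. The effect is too small to change the reading of this pilot, but it is avoidable in figures intended to inform the next trial.

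**What to change.** Amend the 2° Efficacy Outcome paragraph in Section 9:

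1. When the NUI or the concomitant-medication form shows nicotine replacement within the cotinine detection window, confirm 7-day PPA by self-report plus CO, and do not fail the participant on cotinine alone. State the window.
2. Report, as a sensitivity analysis, PPA at weeks 12 and 24 under the unmodified rule of CO plus cotinine.
3. Tabulate use of any non-study cessation aid by arm at weeks 12 and 24. Confirm that both forms are completed at the week-24 visit.

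The direction of the CO limit and the cotinine unit must be corrected in the same paragraph, since the rule cannot be applied as printed.

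The cost is a wording change, one further analysis and one table, from forms already in use. The downside is that CO covers a shorter period than cotinine, so confirmation is weaker for these participants; the sensitivity analysis shows how much depends on it. I would limit the exception to nicotine replacement. Extending it to e-cigarettes and other non-combusted products is a trade-off for the investigators to decide.

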For each feasibility measure we will compare study values to the targeted benchmarks which are based on our prior work in SMI smokers (4,49) and the relevant literature (13,19). While formal hypothesis testing is not planned given the pilot nature of this proposal (50,51), we will calculate effect sizes (i.e., Cohen's d or odds ratios [ORs]) and standard deviations, as well as confidence intervals (CI), for our feasibility variables and use

them as preliminary data for the subsequent larger RCTs. We will also calculate and examine Cohen's kappa coefficients for our clinician-obtained measures including the MINI, TLFB, C-SSRS, and assessments of NPSAEs and general AEs. These values will be used to assess the inter-rater reliability of relevant measures in SMI smokers and to refine our rater training procedures if necessary.

Aim 2: Explore whether nicotine clearance rate as measured by the NMR influences the incidence of NPSAEs in varenicline-treated SMI smokers. This exploratory aim will begin to test the **hypothesis** that incidence of NPSAEs of any severity will be higher in slow nicotine metabolisers assigned to standard dose varenicline compared with normal metabolisers treated with low dose varenicline.

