To gather preliminary data on the NMR, the frequency distributions of the NMR values in this SMI sample will be compared with the published data from Lerman et al. (2015) in a large sample of NMI smokers that found a cutoff score of 0.31 as the demarcating point between slow (<0.31) and normal (including rapid) metabolisers. Based on this analysis, we will calculate Cohen's d effect sizes comparing slow metabolisers on standard dose vs. normal metabolisers on low dose, as well as standard deviations and CIs, for incidence of NPSAEs of any severity to examine the direction and magnitude of the effect. Secondary outcome measures will also be examined using the same methodologies including 7-day PPA at weeks 12 and 24, to guide future studies. Regarding the secondary efficacy outcomes, and anticipating possible quit-boosting effects from ACT and varenicline preloading, we predict 7-day PPA rates at week 12 will be at least comparable to those observed in varenicline-treated EAGLES SMI participants which was 28.2%, and that 7-day PPA rates at week 24 will be at least comparable to the 20.0% observed in EAGLES (unpublished data). To examine the possible confounding effect of variable lengths of abstinence depending on when participants first attempt to quit smoking within the quit window, we will examine the effect of a time factor (i.e., the number of days from the first dose of medication to the date of the first quit attempt) with the methodologies described above.

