Consistent with recommendations on the proper sizing for pilot studies literature (50,51,53), we chose a sample size of 60 participants based on maximal accrual expectations over a 15-month recruitment period and practical cost constraints to conduct a pilot trial in this special population of smokers. Previous studies examining target sample sizes for pilot studies have argued that as few as 12 participants per group is adequate to estimate standard deviations for a two-group study (54,55), while others have suggested that a total sample of 30 is an acceptable size for a pilot study (56). With a sample of 60 (n=30 per dosing group), we will have the ability to estimate effect sizes, standard deviations, and their CIs with adequate precision to evaluate the feasibility of study procedures and to subsequently conduct formal power analyses for future RCTs (57). As such, it is amply sized as a pilot trial. For example, given a small-to-medium estimated effect of $d=0.40$, we would have 80% confidence that the true effect fell between 0.064 and 0.733 with a pilot sample of N=60. For a smaller effect of $d=0.30$, this 80% CI becomes 0.005-0.672 providing adequate precision in detecting an effect (i.e., zero not in the CI) for use in power analyses for a larger RCT. Furthermore, applying Sims' and Lewis' (2012) calculations, the sample size of N=60 will allow us to estimate standard deviations around our feasibility estimates with a minimal inflation factor (e.g., 1.09 for one-sided 80% CIs) for use in future RCT power analyses.

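### Exploratory scales measured at Week 0 are to be compared with no baseline term; ANCOVA on each scale's own Week 0 score would give a modest, low-cost gain in precision

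*Combined protocol and SAP*

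**What the plan says.** All of this is in section 9 of the combined protocol and SAP.

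- **Status of the scales (Other Secondary Outcome Measures).** "Our gathering of data on the MNWS, QSU-Brief, ISI, SEQ-12, Confidence to Quit Scale is exploratory in nature". The stated purpose "is intended to provide preliminary information on the mechanism of action of combined varenicline and ACT in SMI smokers and their relation to NPSAEs". For the AIS: "We will also explore ACT's effects on avoidance and inflexibility with the AIS at weeks 12 and 24".
- **Aim 1 analysis.** "While formal hypothesis testing is not planned given the pilot nature of this proposal"; instead, "we will calculate effect sizes (i.e., Cohen's d or odds ratios [ORs]) and standard deviations", with confidence intervals, for the feasibility variables.
- **Aim 2 analysis.** For NPSAEs of any severity, "we will calculate Cohen's d effect sizes comparing slow metabolisers on standard dose vs. normal metabolisers on low dose". Then: "Secondary outcome measures will also be examined using the same methodologies including 7-day PPA at weeks 12 and 24". The only further explanatory factor named is the number of days from first dose to first quit attempt, which is not a baseline score.
- **Data collected.** The Baseline Visit (Week 0) text for the Red, Orange and Yellow/Green phases lists the MNWS, QSU-Brief, ISI, SEQ-12, Confidence to Quit Scale and AIS each time.
- **Planned precision (Sample Size Determination).** For d = 0.40, "we would have 80% confidence that the true effect fell between 0.064 and 0.733 with a pilot sample of N=60".

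**The concern.** The plan justifies 60 participants by how precisely effect sizes and their intervals can be estimated. For a continuous scale measured before treatment, a comparison that ignores the baseline leaves explainable variation in the error term. The interval is then wider than it need be whenever the baseline score predicts the outcome to a useful degree. The analysis text names no model, no baseline covariate and no choice between endpoint and change scores.

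What is at stake is the width of intervals on exploratory scales. The numbers are small, and smallest in the contrast to which the plan attaches its secondary analyses, so the loss is worth avoiding when the baseline data will already be in hand.

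**Working it through.** **Inputs from the documents.** 60 randomised, 30 per arm (Sample Size Determination); 1:1 allocation (Overview); retention of at least 80% (Hypothesis 1b); slow metabolisers about 40% of smokers without mental illness (section 7).

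**Assumptions.** Baseline-outcome correlation r = 0.3, 0.5 or 0.7, with r = 0 as the worst case. Retention sits exactly at the 80% benchmark. The 40% slow share carries over to this population.

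**1. The plan's own figure.** The exact noncentral-t 80% interval for d = 0.40 with 30 per arm is 0.0640 to 0.7326, which matches the stated 0.064 to 0.733. The half-width is (0.733 − 0.064)/2 = 0.3345. This is an unadjusted interval on all 60. With 24 per arm it becomes 0.024 to 0.772, half-width 0.374.

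**2. Group sizes.**
- Dose arms: 0.80 × 60 = 48, or 24 v 24.
- Metaboliser contrast: 0.40 × 30 = 12 slow on standard dose and 0.60 × 30 = 18 normal on low dose. At 80% retention these are 9.6 and 14.4, taken as 10 v 14, total 24.

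**3. ANCOVA against unadjusted endpoint scores.** With one covariate,

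equivalent N = N/(1 − r²) × (N − 4)/(N − 3).

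The last factor is the price of estimating the slope.

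| Contrast | r = 0 | r = 0.3 | r = 0.5 | r = 0.7 |
|---|---|---|---|---|
| 10 v 14 (N = 24) | 22.9 | 25.1 | 30.5 | 44.8 |
| 24 v 24 (N = 48) | 46.9 | 51.6 | 62.6 | 92.0 |

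For example, with N = 48 and r = 0.5: 48/0.75 × 44/45 = 62.6. Simulation of the mean 80% t-interval agrees to within 0.1. In SD units the half-width goes from 0.541 unadjusted to 0.529, 0.480 or 0.396 for 10 v 14, and from 0.373 to 0.360, 0.327 or 0.270 for 24 v 24. Adding diagnosis to the 24 v 24 model gives 51, 62 and 91, and to the 10 v 14 model 23.7 at r = 0.3. In these simulations diagnosis brought no benefit.

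**4. Break-even.** The adjustment pays when r² > 1/(N − 3). That is r > 1/√21 = 0.22 for N = 24 and r > 1/√45 = 0.15 for N = 48. At r = 0 the loss is 24 − 22.9 = 1.1 or 48 − 46.9 = 1.1 participants.

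**5. If d were computed on change scores.** Relative to endpoint scores, 48 would act like 48/(2(1 − r)) = 34, 48 or 80. ANCOVA relative to change scores gives 48 × 2/(1 + r) × 44/45 = 72, 63 or 55. At r = 0.7 most of the gain is therefore already in the change score; at r = 0.3 the change score is the worst of the three.

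**6. Link to the planned precision.** At r = 0 the adjusted half-width for 24 v 24 is 0.378. It returns to 0.3345 when √(1 − r²) = 0.3345/0.378, so r = 0.47.

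**The case against.** The strongest case against is that the larger figures belong to an analysis the plan does not contain. Aim 1's effect sizes are for feasibility variables. The Aim 2 sentence on secondary measures follows the slow/standard versus normal/low contrast. The purposes given for the scales are the mechanism of a combined treatment and a relation to NPSAEs. Both arms receive varenicline and ACT, so neither purpose is a low-versus-standard comparison. This stands: a reader might infer that the plan commits to an inefficient dose-arm comparison of these scales, but it specifies none. The 48-participant figures apply only if one is reported, and the AIS is covered only if it is compared between groups.

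The gain is also conditional. No document gives r, and it could be low: baseline scores come from active smokers, while some will have stopped by follow-up. The top of the range needs endpoint scores as comparator and r = 0.7. That stands too, and is why the break-even and the change-score figures are shown.

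A reader might infer from the marks in Table 3 that the baseline visit is ambiguous for some scales. The documents do not support that reading. The Baseline Visit text names Week 0 and lists every scale there. Table 3 in the text available for this review lacks a Week 24 column, so the position of its marks cannot be relied on.

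Finally, ANCOVA at a single visit is not the only sensible model; a repeated-measures model carrying the Week 0 score would also serve. That is fair, but it does not remove the case for a baseline term.

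**Conclusion.** The point holds as a low-severity improvement in precision for exploratory scales. In the contrast the plan attaches to its secondary measures, 24 retained would act like about 25, 30 or 45 at r = 0.3, 0.5 or 0.7. In a dose-arm contrast, if one is reported, 48 would act like about 52, 63 or 92. Both ranges rest on assumed correlations, 80% retention and an endpoint-score comparator; the first also assumes 40% slow metabolisers. At r = 0.3 the gain in the metaboliser contrast is about one participant, and below r of about 0.2 there is a loss of similar size.

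Three stronger readings are not supported:

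- **Bias.** The unadjusted randomised dose-arm difference is unbiased; only its precision is at issue.
- **Primary aims or later sizing.** Feasibility benchmarks, NPSAE incidence and 7-day abstinence do not use these scores, so neither the trial's main conclusions nor the sizing of a later trial on NPSAEs or abstinence changes.
- **Confounding.** Baseline adjustment does not make the slow/standard versus normal/low contrast a clean comparison. Dose and metaboliser status differ together in it, with or without a covariate.

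**What to change.** Add to the Data Analytic Plan: wherever a between-group difference in the MNWS, QSU-Brief, ISI, SEQ-12, Confidence to Quit Scale or AIS is reported, estimate it by ANCOVA on group and that scale's own Week 0 score, give its confidence interval, and show the unadjusted value alongside. Apply this to the slow/standard versus normal/low contrast, with a statement that confounding of dose with metaboliser status remains, and to any low-versus-standard contrast. If the result is expressed as Cohen's d, say which SD standardises it; the Week 0 SD would do. Report the baseline-outcome correlation and residual SD, which are useful for planning any later study that uses these scales. Leave the analyses of feasibility, NPSAE incidence and 7-day abstinence as they are.

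The cost is a sentence or two of SAP text, a few lines of code and one degree of freedom per model. No new data are needed. If the baseline turns out to be uninformative, the loss is about one participant's worth of precision.
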